postprocedural ischemic stroke or death. The detailed information is as follows:

- A thromboembolism detected during the neurointerventional procedure
- Transient ischemic attack, ischemic stroke, or death with evidence of infarction on diffusion-weighted imaging, occurring within 30 days after the procedure

The secondary endpoints were postprocedural stroke and diffusion-restricted lesions on diffusion-weighted MRI. Another secondary endpoint was the preprocedural platelet function test value and its adjustment ratio. The details are as follows:

- Ischemic stroke in the relevant arterial territory within 30 days after the procedure
- Any stroke, including ischemic and hemorrhagic strokes, within 30 days after the procedure
- Disabling or fatal stroke within 30 days after the procedure
- Diffusion-restricted lesion detected on the 7-day postprocedural MRI

The safety endpoints were bleeding related to P2Y12 antagonists, including any bleeding within 30 days or major bleeding. Bleeding criteria followed the PLATelet inhibition and patient Outcomes bleeding criteria [4,5].

- Major bleeding criteria
 - ✓ Fatal bleeding (bleeding that directly results in death within 7 days)
 - ✓ Intracranial bleeding
 - ✓ Intrapericardial bleeding with cardiac tamponade
 - ✓ Hypovolemic shock or severe hypotension due to bleeding, requiring pressors or surgery
 - ✓ A decline in the hemoglobin level of ≥ 5.0 g/dL
 - ✓ Need for transfusion of at least 4 units of red blood cells
- Other major bleeding criteria
 - ✓ Bleeding that led to clinically significant disability
 - ✓ Decline in hemoglobin level of ≥ 3.0 g/dL but < 5.0 g/dL
 - ✓ Need for transfusion of at least 2-3 units of red blood cells
- Minor bleeding criteria
 - ✓ Any bleeding requiring medical intervention but not meeting the criteria for major bleeding

Determination of the Sample Size

Given the hypothesis of the present study, we used a two-proportion Z-test with pooled variance and set the significance level at 0.05, power = 0.8.

In previous retrospective studies, intraprocedural thromboembolism occurred in the prasugrel group (0.009) and the clopidogrel group (0.064), with a -0.055 difference in the ratio of any stroke and death during the 30-day treatment. A total of 182 samples were required to prove significance at 80% for each group. Considering the 10% dropout rate, 203 patients were required per group, with a total of 406 patients.

Statistical Analysis

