Prasugrel and clopidogrel are widely used for treating cardiovascular diseases, and clopidogrel is the standard treatment for cerebrovascular diseases. In the case of prasugrel, a maintenance dose of 10 mg is used for patients with acute myocardial infarction, and a maintenance dose of 5 mg is used for those aged \geq 75 years or those weighing <60 kg [6]. For participants in whom clopidogrel will be used, it will be beneficial to proceed with the established standard treatment; it has been reported that subjects using prasugrel have a lower level of drug resistance than the known resistance to the platelet action of clopidogrel due to the pharmacological mechanism. A higher drug effect is expected compared with clopidogrel.

Both clopidogrel and prasugrel may increase the risk of bleeding; however, this is the standard treatment guideline recommended for patients because the risk of treatment complications is not higher than that of the procedure. A retrospective study published in 2018 reported that low-dose prasugrel (5 mg) caused lower ischemic complications than 75 mg clopidogrel (0.9% vs. 6.4%, $P = 0.011$), and hemorrhagic complications were statistically significant. No significant difference was reported (0.5% vs. 2.2%, $P = 0.218$). Therefore, it cannot be concluded that the risk was particularly high in the prasugrel group in this study.

Definition of Adverse Events (AEs)

An AE is defined as any unintended or undesirable sign, symptom, or disease, regardless of whether it is associated with therapy or a drug. AEs will be evaluated from the time of providing informed consent and followed until resolution. An ongoing AE at the last visit will be followed up until the event is resolved or stabilized.

Serious AEs are defined as any event occurring during the study and are considered related to the study.

- ✓ Death
- ✓ Life-threatening condition

- ✓ Permanent or significant disability/incapacity/congenital anomalies/birth defects
- ✓ Result in hospital admission or prolonged hospital stay

In the event of unexpected or unpredictable AEs due to additional procedures and interventions, we considered the best possible treatment so that the study participants could receive appropriate medical treatment. If an adverse event occurs, it will be recorded in the adverse report form attached to the case record, and the principal investigator will report it to the Institutional Review Board Secretariat within 24 h of being recognized.

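### The serious adverse event definition requires relatedness to the study, so serious events judged unrelated are not classed as serious; the bleeding endpoint carries similar, ambiguous wording.

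*Combined protocol and SAP*

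**What the plan says.** In the combined protocol and SAP, Definition of Adverse Events (AEs), the general definition has no causal condition: "An AE is defined as any unintended or undesirable sign, symptom, or disease, regardless of whether it is associated with therapy or a drug". The serious category adds one: "Serious AEs are defined as any event occurring during the study and are considered related to the study". The list beneath it covers death, life-threatening conditions, lasting disability or congenital anomaly, and admission or a longer hospital stay. The section does not say who judges relatedness or by what criteria. On recording, it says: "If an adverse event occurs, it will be recorded in the adverse report form attached to the case record". The principal investigator then reports the event to the review board within 24 hours.

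Under Study Endpoints, the safety endpoint is worded: "The safety endpoints were bleeding related to P2Y12 antagonists, including any bleeding within 30 days or major bleeding". The grading rule follows: "Bleeding criteria followed the PLATelet inhibition and patient Outcomes bleeding criteria". The detailed primary endpoint limits death by an imaging finding: "or death with evidence of infarction on diffusion-weighted imaging". Statistical Analysis applies between-arm tests to the primary, secondary and safety endpoints. It does not mention serious AEs or all-cause death.

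**The concern.** Seriousness describes what happened to the patient. Relatedness is an opinion about why. The definition joins the two, so the opinion decides the classification. Safety is one of the two things the trial sets out to compare. A reader of the results will expect a count of serious AEs by arm to hold every death and every life-threatening event, and under this wording it would hold only those that someone attributed to the study.

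The matter is sharper if the person judging knows the treatment. The detailed study protocol sets arm-specific regimens and an arm-specific adjustment at PRU ≥220, and no placebo is described, so treating staff probably know the arm. A judgment made with that knowledge can differ between arms without anyone intending it.

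The bleeding endpoint raises the same question in a place that is tested. If relatedness to the P2Y12 antagonist is a condition for counting a bleed, that endpoint too depends on an undefined attribution.

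**Working it through.** The point concerns definitions, so the check is a side-by-side reading. The plan's only design calculation (182 per group, 203 after 10% dropout) reproduces and does not depend on this point.

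**1. AE against serious AE.** An AE qualifies "regardless of whether it is associated with therapy or a drug". A serious AE must be considered related. Take a death in the follow-up period that the assessor thinks has nothing to do with the study. It meets the AE definition and the first listed outcome, but fails the relatedness condition. Result: an AE, not a serious AE. The same holds for each other listed outcome.

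**2. Is the event lost?** No. Recording and board reporting apply to any adverse event, related or not. The event is in the case record under the wrong class.

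**3. Does a planned test use the serious AE class?** No. The tested safety endpoint is bleeding. Stroke and death with infarction are counted under their own definitions. None of these refers to serious AE status.

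**4. Which deaths have no other place?** Working through the detailed definitions:

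| Type of death within 30 days | Captured by |
|---|---|
| Infarction on diffusion-weighted imaging | Primary endpoint |
| Fatal stroke | Secondary endpoint |
| Death directly from bleeding within 7 days | Major bleeding |
| Other death, judged related | Serious AE only |
| Other death, judged unrelated | AE only |

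The last row is the gap. It depends on the detailed wording: the sentence that introduces the primary endpoint names death without the imaging condition, and on that broader reading the row would be in the primary endpoint.

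**5. The bleeding wording.** The listed criteria grade a bleed by site, haemoglobin fall, transfusion or need for intervention. None asks which drug caused it. The lead-in, "The safety endpoints were bleeding related to P2Y12 antagonists", can be read as describing the kind of bleeding of interest or as a condition for counting. Under the second reading the arms differ: at PRU ≥220 cilostazol is added in the clopidogrel group only, whereas the prasugrel group receives more of its assigned drug. A second drug to which a bleed could be attributed is therefore added in one arm only. As written this period is short, because the discharge medication for the clopidogrel group does not list cilostazol. Aspirin is common to both arms.

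**6. Can a bias be computed?** Not from the documents. It would need a serious AE rate and the share judged related in each arm, and neither is given.

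**The case against.** The strongest case against the point is that nothing tested depends on the definition. The important harms in this setting (intracranial or fatal bleeding, shock, transfusion, stroke, death with infarction) are endpoints in their own right, and every other event is still on the adverse report form. This stands, and it limits the severity. It does not make the definition correct, because reporting an event to the review board does not change how it is classified.

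The serious AE sentence is also loosely built. It could be read as saying that serious AEs are all presumed related. That reading would not exclude any event, but it would still merge outcome with cause, and the same edit would resolve it.

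Three stronger conclusions are tempting and are not supported:

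- **That relatedness judgments decide which serious harms enter the safety comparison.** No between-arm comparison of serious AEs is planned. The most that can be said is that any serious AE tabulation would inherit the problem.
- **That the false-positive risk can be stated.** Suppose 203 per arm, equal true rates, all clopidogrel events and 75% of prasugrel events rated related, and a two-sided Pearson test at 5%. Exact binomial enumeration then puts the chance of a significant result favouring prasugrel at 3.4% for an assumed true rate of 1% and 13.8% for 10%, against about 2% to 2.4% with no differential rating. Every input except the group size and the test is invented, the direction is chosen, and the plan contains no such test. These figures say nothing about this trial.
- **That the trial is open-label.** The Randomization section says a third party managed allocation so that researchers were blinded to it. Arm-specific regimens make knowledge of the arm by treating staff likely, but the supplied text contains no open-label statement and does not say who judges relatedness.

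On bleeding, it is fair to reply that a clopidogrel patient given cilostazol is still taking clopidogrel and that no rule excludes such a bleed. The wording is therefore ambiguous, not shown to be wrong.

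**Conclusion.** The serious AE definition is wrong as written. It sits directly below an AE definition that disregards cause, and it makes seriousness depend on a judgment with no named assessor and no criteria. Events judged unrelated are misclassified, not lost. Severity is modest: no planned test uses the class, and no numerical bias follows from the documents.

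Two consequences remain. Under the detailed endpoint definitions, a death that is not due to bleeding or stroke, shows no infarction on diffusion-weighted imaging and is judged unrelated is neither an endpoint nor a serious AE. And the bleeding endpoint, which is tested, has attribution wording that should be settled before anyone counts events. The conclusion assumes that the serious AE sentence is applied literally. The concern about arm-dependent judgment also assumes that the assessor knows the arm, which is probable but not stated.

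**What to change.** 1. In Definition of Adverse Events (AEs), delete the relatedness clause and define a serious AE as any AE that meets at least one listed outcome, regardless of cause.
2. Record relatedness as a separate field, and state who assesses it and by what criteria.
3. Add to Statistical Analysis a report of all-cause deaths and all serious AEs by arm, with related serious AEs as a subset.
4. In Study Endpoints, define the bleeding endpoint as every bleed within 30 days that meets the listed criteria, whatever drug it is attributed to.

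The cost is a short text correction, one extra form field and two rows in a safety table. Reported serious AE and bleeding counts may be somewhat higher. No extra visits or patients are needed, and because all AEs are already recorded, events collected so far can be reclassified.
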